•	To evaluate the treatment benefit of erenumab on duration of migraine pain of at least moderate intensity in months with at least 1 migraine attack (migraine attacks as defined in Section 11.1)	•	Change from baseline in mean monthly average duration of at least moderate pain intensity per migraine attack over months 1, 2, and 3	
•	To evaluate the treatment benefit of erenumab on peak migraine pain intensity in months with at least 1 migraine attack (migraine attacks as defined in Section 11.1)	•	Change from baseline in mean monthly average peak migraine pain intensity as assessed by the 11-point NRS over months 1, 2, and 3	
Ex	ploratory Double-blind Treatment Phase	(mor	nth 4)	
•	To evaluate the treatment benefit of erenumab on interictal burden of migraine	•	Change from baseline in Migraine Interictal Burden Scale (MIBS-4) total score at month 4	
For the first qualifying oral triptan-treated attack (defined in Section 11.1) with complete data at 2-hour assessment:				
•	To evaluate the treatment benefit of erenumab on achieving and	•	Achievement of pain freedom at 2 hours post-triptan dose for the first attack at month 4	
	sustaining pain freedom following treatment with an oral triptan		Achievement of 24-hour sustained pain freedom post-triptan dose for the first attack at month 4	
		•	Achievement of pain freedom at 30 and 60 minutes post-triptan dose for the first attack at month 4	
•	To evaluate the treatment benefit of erenumab on achieving pain relief following treatment with an oral triptan	•	Achievement of pain relief (defined in Section 11.1) at 30, 60, and 120 minutes post-triptan dose for the first attack at month 4	

•	To evaluate the treatment benefit of erenumab on achieving freedom from the most bothersome symptom following treatment with an oral triptan	•	Achievement of freedom from the most bothersome symptom at 30, 60, and 120 minutes post-triptan dose for the first attack at month 4
•	To evaluate the treatment benefit of erenumab on achieving relief from the most bothersome symptom following treatment with an oral triptan	•	Achievement of relief from the most bothersome symptom at 30, 60, and 120 minutes post-triptan dose for the first attack at month 4
•	To evaluate the treatment benefit of erenumab on migraine recurrence following treatment with an oral triptan	•	Migraine recurrence (defined in Section 11.1) during 24 hours post-triptan dose for the first attack at month 4

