Migraine recurrence	return of any headache of at least moderate pain intensity in patients who were pain-free at 2 hours post-dose
MMD	monthly migraine days
MSSS	Migraine Symptom Severity Score
NCT	National Clinical Trials
NRS	Numeric Rating Scale
pain relief	reduction from moderate/severe pain to mild/no pain
PCS	Pain Catastrophizing Scale
PFS	prefilled syringes
PGI-S	Patient Global Impression of Severity
PHQ-9	Patient Health Questionnaire
Q4W	every 4 weeks
QM	once monthly
Qualifying oral triptan-treated attacks (run-in period/month 4)	migraine attacks of at least moderate peak pain intensity that are treated with an oral triptan within 2 hours of pain reaching at least moderate severity
Qualifying oral triptan-treated attacks (baseline/ month 1, 2, and 3)	migraine attacks that are treated with an oral triptan
Randomization	defined as the day a subject has met all run-in and baseline period eligibility criteria and is enrolled and randomized into the study (subjects are enrolled same day)
SAP	statistical analysis plan
SC	subcutaneous(ly)

Abbreviation or Term	Definition/Explanation
Source d ata	information from an original record or certified copy of the original record containing patient information for use in clinical research. The information may include, but is not limited to, clinical findings, observations, or other activities in a clinical trial necessary for the reconstruction and evaluation of the trial. Source data are contained in source documents (original records or certified copies). (ICH Guideline [E6]). Examples of source data include Subject identification, Randomization identification, and Stratification Value.
Study d ay 1	defined as the first day that protocol-specified investigational product(s)/protocol-required therapies is/are administered to the subject
Total migraine freedom days	Days where there is an absence of headache and aura, photophobia, phonophobia, and nausea/vomiting
US	United States

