5.1.2 Efficacy Endpoints Based on Episodic Diary Data Collection During E-DBTP

During the 2-week run-in period and the 1-month E-DBTP at month 4, subjects experiencing a qualified triptan-treated migraine attack will report medication usage, pain intensity, the most bothersome symptom and corresponding severity using the episodic diary. A qualifying headache for reporting is a headache reaching at least moderate pain intensity with initial triptan intake within 2 hours and also satisfying migraine headache criteria (ie, a qualified triptan-treated migraine attack). The initial triptan intake time (ie, time point 0) will trigger a 48-hour assessment window, during which the headache pain intensity, severity of the most bothersome symptom at 30, 60 and 120 minutes, 24 hours and 48 hours post triptan will be collected. Another 48-hour assessment window will be triggered if there is a new qualified triptan-treated migraine attack starts after the previous assessment window.

Headache Pain Intensity (NRS) in E-DBTP

Worst or peak pain intensity collected on a headache ranges from 0 to 10 with a higher score indicating more severe pain.

NRS Pain intensity is collected when a qualified headache reaching at least moderate pain intensity with triptan intake within 2 hours and for the following timed assessments at 30 minutes, 1-hour, 2-hour, 24-hour and 48-hour diaries.

Migraine Rescue Medication

Migraine rescue medication for each qualifying triptan-treated attack is defined as any additional acute headache medication(s) taken during the 48-hour assessment window.

Migraine Recurrence Within 24 Hours Post-triptan

Pain intensity NRS = 0 at any of the 30-minute, 60-minute, and 2-hour timed assessments and pain intensity NRS \geq 4 at 24-hour timed assessment

Pain Relief at timed assessment post-triptan dose

Pain intensity NRS < 4 at the specific timed assessment (eg, 30 minutes, 60 minutes, or 2 hours post-triptan dose).

Pain freedom at timed assessment post-triptan dose

Pain intensity NRS = 0 at the specific timed assessment (eg, 30 minutes, 60 minutes or 2 hours post-triptan dose).

Achievement of 24-hour sustained pain freedom post-triptan dose

Pain intensity NRS = 0 at both 2-hour and 24-hour timed assessment without rescue medication taken post-triptan dose.

Most Bothersome Symptom

The most bothersome symptom can be selected among nausea, vomiting, sensitivity to light, or sensitivity to sound.

Severity of Most Bothersome Symptom (4-level)

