8.3 Handling of Missing and Incomplete Data

Subjects may miss specific data points for a variety of reasons. In general, data could be missing due to a subject's early withdrawal from the study, a missed visit, or inability to evaluate an endpoint at a time point. For this study, efficacy endpoints will be collected via eDiary and subjects could miss entering several days of data in each monthly interval. The general procedures outlined below describe how missing data will be handled.

For the endpoints derived from the daily diary data, please refer to proration approach specified in Section 5.1.1 on handling missing daily diary data. Missing monthly measurement after proration will be handled by statistical analysis approaches listed in Section 9.5.

For the endpoint derived from the episodic diary data, missing data at timed assessment will be handled by statistical analysis approaches listed in Section 9.5.

Missing items in each clinical outcome assessment questionnaire will be handled based on the scoring algorithm for each assessment. The missing value in the algorithm derived measurements (eg, total score, domain scores) will be handled by statistical analysis approaches listed in Section 9.5.

Missing data in safety endpoints will not be imputed except for incomplete start date of an AE or concomitant medication, which will be imputed as follows:

	Missing	Imputation	Exception on adverse event start date
Start date (AE, concomitant medication)	Day	01	Default to Study Day 1 if an adverse event started the same year and month as Study Day 1 and the flag indicates that the adverse event started on or after the first dose of investigational product on the Events eCRF
	Day/Month	01 JAN	Default to Study Day 1 if an adverse event started the same year as Study Day 1 and the flag indicates that the adverse event started on or after the first dose of investigational product on the Events eCRF
	Day/Month/Year	No imputation	-

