Change from baseline in social function domain as measured by MFIQ at assessment time points Change from baseline in emotional function domain score as measured by MFIQ at assessment time points

Change from baseline in overall impact on usual activities global item score as measured by MFIQ at assessment time points

Change from baseline in mean monthly average duration of at least moderate pain intensity per migraine attack in months with at least 1 migraine attack

Change from baseline in mean monthly peak migraine pain intensity as assessed by the 11-point Numeric Rating Scale (NRS) in months with at least 1 migraine attack

^b The same analyses methods will be applied to the endpoints: Change in Patient Global Impression of Severity (PGI-S) total score at month 3

^c The same analyses methods will be applied to the endpoints: Change from baseline in the most troublesome symptom (MTS) at month 3

 ^d The same analyses methods will be applied to the endpoints: Achievement of pain freedom at 30 and 60 minutes post-triptan dose for the first attack at month 4 Achievement of pain relief at 2 hours post-triptan dose for the first attack at month 4 Achievement of freedom from the most bothersome symptom at 30, 60, and 120 minutes post-triptan dose for the first attack at month 4 Achievement of relief from the most bothersome symptom at 30, 60, and 120 minutes post-triptan dose for the first attack at month 4 Achievement of 24-hour sustained pain freedom post-triptan dose for the first attack at month 4 Migraine recurrence during 24 hours post-triptan dose for the first attack at month 4

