9.5.3 E-DBTP Analyses of Exploratory Efficacy Endpoints

The dichotomous efficacy endpoints for assessing qualifying triptan-treated attacks only in E-DBTP will be analyzed using logistic regression model with missing data imputed as non-responders (NRI) **up to End of Study Date**. Odds ratios of treatment group and placebo with associated 95% CIs and p-values will be reported. The efficacy endpoint for Migraine Interictal Burden Scale at month 4 will be analyzed using the linear mixed effects model that includes treatment group, baseline values, scheduled visit, and the interaction of treatment and scheduled visit without any imputation for missing data.

The following exploratory endpoints of the E-DBTP for the first qualifying triptan-treated attack will be analyzed by medication overuse status at month 3 (yes vs. no):

- Achievement of pain freedom at 2 hours post-triptan dose for the first attack at month 4
- Achievement of pain relief at 2 hours post-triptan dose for the first attack at month 4
- Achievement of relief from the most bothersome symptom at 30, 60, and 120 minutes post-triptan dose for the first attack at month 4
- Achievement of 24-hour sustained pain freedom post-triptan dose for the first attack at month 4
- Migraine recurrence within 24 hours post-triptan dose for the first attack at month 4
- Use of migraine rescue medication within 24 hours post-triptan dose for the first attack at month 4

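### Exploratory month-4 migraine recurrence: the SAP admits patients pain-free only at 30 or 60 minutes, whom the protocol excludes, and does not state the value imputed for a missing outcome

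*SAP*

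**What the plan says.** The protocol's table of objectives and endpoints (Section 3) names the endpoint as "Migraine recurrence (defined in Section 11.1) during 24 hours post-triptan dose for the first attack at month 4". Section 11.1 defines recurrence as "return of any headache of at least moderate pain intensity in patients who were pain-free at 2 hours post-dose".

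SAP 5.1.2 opens its definition differently: "Pain intensity NRS = 0 at any of the 30-minute, 60-minute, and 2-hour timed assessments". It then requires NRS 4 or more at the 24-hour assessment. In the same section, 24-hour sustained pain freedom requires NRS 0 at both 2 and 24 hours. SAP Section 10 declares one departure from the protocol, the split of the efficacy analysis set.

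On missing data, protocol 9.3.4 imputes non-response for binary endpoints. SAP 8.3 says that "missing data at timed assessment will be handled by statistical analysis approaches listed in Section 9.5". There, Table 9-3 footnote d lists "Migraine recurrence during 24 hours post-triptan dose for the first attack at month 4" and so gives recurrence the method used for 2-hour pain freedom: logistic regression with missing values set to non-response (NRI). SAP 9.5.3 has the dichotomous triptan-attack endpoints "analyzed using logistic regression model with missing data imputed as non-responders (NRI", and its list of endpoints for analysis by medication overuse includes "Migraine recurrence within 24 hours post-triptan dose for the first attack at month 4". Rescue medication, the other unfavourable event, has its own Table 9-3 row and is analysed on observed data.

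**The concern.** The two documents define different at-risk groups for an endpoint of the same name. Under the SAP, an attack in which pain went away briefly and was back by 2 hours can count as a recurrence. That attack also fails 2-hour pain freedom, so one treatment failure is reported under two endpoints. The SAP's sustained pain freedom and recurrence endpoints, which ought to describe the same starting group, no longer do so.

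The imputation gap is smaller. Non-response is clear for something a patient achieves, but for an unfavourable event the imputed value has to be written down. The index attack is the first with complete data at 2 hours, so missing values should arise mainly at 24 hours, where recurrence is read. SAP 9.5.3 promises an odds ratio, confidence interval and p-value for the dichotomous triptan-attack endpoints, and the documents name no sensitivity analysis for recurrence that would show how far its result depends on the choice.

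**Working it through.** The plan gives no rate, sample size or power for recurrence, so there is no figure to reproduce. The definitions can be compared directly; the sizes below rest on assumed rates.

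**1. Definitions side by side**

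| | Protocol Sections 3 and 11.1 | SAP 5.1.2 |
|---|---|---|
| Pain-free state required | at 2 hours | at any one of 30 minutes, 60 minutes, 2 hours |
| Event | return of at least moderate headache during 24 hours | NRS 4 or more at the 24-hour assessment |

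**2. Three attacks classified**

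| Attack | Protocol | SAP |
|---|---|---|
| NRS 0 at 30 min, 5 at 2 h, 5 at 24 h | not at risk | recurrence |
| NRS 0 at 2 h, 6 at 24 h | recurrence | recurrence |
| never 0, 6 at 24 h | not at risk | no recurrence |

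The first row is the conflict, and it needs no assumption.

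**3. How many extra events (assumed rates, per 100 first qualifying attacks)**

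- Protocol events: 35 pain-free at 2 hours × 0.25 relapsing = 8.75.
- If x attacks are pain-free only before 2 hours and 30% to 60% of them score 4 or more at 24 hours, the SAP adds 0.3x to 0.6x events.
- x = 0 adds none. x = 2 to 5 adds 2 × 0.3 = 0.6 to 5 × 0.6 = 3.0, which is 7% to 34% of 8.75.

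The documents give no value for x.

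**4. Value imputed for a missing outcome**

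Let p be the proportion pain-free at 2 hours (0.35), r the recurrence rate among them, and m the proportion of them without a 24-hour value. The denominator is all first qualifying attacks. An attack never pain-free is a non-event whatever its 24-hour value.

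- Missing = no recurrence: event rate a = p·r(1 − m).
- Missing = recurrence: event rate a = p·[r(1 − m) + m].
- Odds ratio, erenumab v placebo = [a_E/(1 − a_E)] / [a_P/(1 − a_P)].

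With r = 0.25 in both arms and m = 0.20 v 0.10:

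- No recurrence: 0.35 × 0.20 = 0.0700 v 0.35 × 0.225 = 0.0788; odds ratio 0.88.
- Recurrence: 0.35 × 0.40 = 0.1400 v 0.35 × 0.325 = 0.1138; odds ratio 1.27.

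Other cases by the same formulas:

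| r, E v P | m, E v P | Missing = none | Missing = recurrence |
|---|---|---|---|
| 0.25 v 0.25 | 0.10 v 0.05 | 0.94 | 1.15 |
| 0.25 v 0.25 | 0.10 v 0.10 | 1.00 | 1.00 |
| 0.20 v 0.25 | 0.20 v 0.10 | 0.69 | 1.12 |
| 0.20 v 0.25 | 0.10 v 0.10 | 0.79 | 0.85 |

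**5. Denominator**

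The SAP does not say whether recurrence is reported over all first attacks or over those that became pain-free; the E-DBTP analysis set is everyone given the week-12 dose. Restricting the case worked in step 4 to patients pain-free at 2 hours (p = 1) gives 0.2000 v 0.2250, odds ratio 0.86, or 0.4000 v 0.3250, odds ratio 1.38.

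**The case against.** Four objections have force.

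- **The SAP is clear on its own terms.** Analysis code follows the SAP, so its entry condition would be programmed consistently. That is true, but the result would not be the endpoint that the protocol names and defines, and Section 10 does not say so. Only part of the SAP's revision history was available, so the statement that the change is undeclared rests on Section 10, which is where it belongs.
- **The extra events may be few.** Criterion 108 and exclusion 210 select against patients who usually become pain-free within an hour. This stands: the 7% to 34% range shows how the count scales and is not an estimate.
- **Non-responder ordinarily means failure, which here is recurrence.** This also stands. A reader might infer that both codings are equally open and that the reported effect will change sign. The documents do not support that: the opposite coding would score a non-responder as a success, and the reversal needs unequal missingness that nothing in the plan predicts. With equal missingness both codings stay on the same side of 1.
- **Observed-data analysis would itself depart from protocol 9.3.4.** Correct. Protocol 9.4.2 leaves exploratory methods to the SAP but does not cancel the imputation rule. The existing rescue-medication row already departs from it without a declaration.

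A reader might also infer that the SAP misses relapses that resolve before 24 hours. That follows only if the 24-hour item is a momentary rating. SAP 5.1.2 describes the score as "Worst or peak pain intensity collected on a headache ranges from 0 to 10 with a higher score indicating more severe pain" and gives no recall period, so this is a question and not a finding.

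**Conclusion.** The conflict over the entry condition is established from the text alone: the protocol requires freedom from pain at 2 hours, the SAP does not, and Section 10 is silent. Its numerical effect is unknown and may be small.

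The imputation point is secondary. The SAP should state the imputed value, but the ordinary reading is recurrence, and the choice matters mainly if missingness differs by arm. The illustrative odds ratios of 0.88 and 1.27 depend on 35% pain-free at 2 hours, 25% recurrence in both arms, 20% v 10% missing and all first attacks as denominator; none of these comes from the documents.

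Rescue medication shows a related mismatch: Table 9-3 uses observed data, while SAP 9.5.3 states NRI without exception. Because SAP 9.5 places the detailed methods in its tables, a reader has grounds to follow the table. The texts do not show how the difference arose.

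Severity is minor. The endpoint is exploratory and outside the sequential testing procedure, so the primary and secondary conclusions are unaffected.

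**What to change.** 1. In SAP 5.1.2, require NRS 0 at 2 hours for recurrence, as in protocol 11.1. State the denominator: either all first qualifying attacks or those pain-free at 2 hours. The second is a subset formed after randomization and should be labelled descriptive.
2. Choose one rule for missing data. Either keep NRI, as protocol 9.3.4 has it, and state that a missing 24-hour value in a patient pain-free at 2 hours counts as recurrence; or analyse observed data, as Table 9-3 does for rescue medication, and declare in Section 10 the departure from protocol 9.3.4 for both endpoints. In either case report the number of missing 24-hour values by arm and make SAP 9.5.3 agree with Table 9-3.
3. As a query, confirm the recall period of the 24-hour NRS item and state it in SAP 5.1.2.

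The cost is SAP wording and code for one exploratory endpoint, and an alignment of 9.5.3 that also covers rescue medication. The assessments are already planned, so no new data are needed.

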9.5.1 Analyses of Primary and Secondary Efficacy Endpoints

For the primary and secondary endpoints will be tested using a linear mixed model based on observed monthly data with appropriate contrasts for pairwise treatment comparisons.

The model will include treatment, scheduled visit, treatment by visit interaction, and baseline value as covariates. If applicable, the first-order autoregressive covariance structure is assumed. Least squares means (LSMs) for each treatment group, standard errors, associated 95% CIs, difference of LSMs compared to placebo group, associated 95% CIs and nominal two-sided p-values will be tabulated by visit and treatment, as well as for the mean monthly values over months 1, 2, and 3 of the DBTP. No sensitivity analyses will be performed for the primary and secondary endpoints.

Subgroup analysis described below will be performed for the primary and secondary endpoints:

- 1. Treatment failure of prior migraine prophylactic medications (1, 2, and 3 or more treatment failures)
- 2. Medication overuse at baseline (yes vs. no)

The purpose of the subgroup analyses is to explore if the treatment effect varies across subgroups of interest. Subgroup analyses are performed for primary and secondary efficacy endpoints using the same method as primary analysis method but performed within each interested subgroup.

The heterogeneity of the treatment effect across the subgroups will be evaluated by examining the treatment-by-subgroup interaction at primary time point and an interaction p-value will be presented. The primary analysis model with the addition of treatment-by-subgroup interaction will be used.

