4.2.2 Number of Sites

Approximately 76 investigative sites in North America and Europe will be included in the study. Sites that do not enroll subjects within 3 months of site initiation may be closed.

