6.4 Measures to Minimize Bias: Randomization and Blinding

6.4.1 Method of Treatment Assignment

Subjects will be randomized in a 1:1 allocation ratio to either erenumab or placebo in a double-blind manner after meeting all the post-baseline randomization requirements described in Section 5.5.

The randomization number will be assigned by the IRT. The randomization number is different than the subject identification number and will not be used by the site as a subject identifier.

The randomization date is to be documented in the subject's medical record and on the enrollment CRF.

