3.2 Sample Size

A total sample size of 576 subjects (288 subjects per group including 10% dropouts) provides at least a 90% power for the primary efficacy hypothesis. The statistical power for secondary efficacy hypotheses ranges from 81% to > 99% (Table 3-1).

Table 3-1. Sample Size Assumptions and Statistical Powers for Primary and
Secondary Efficacy Endpoints for a Total Sample Size of 576 Subjects
Including a 10% Attrition Rate due to Dropout

Hypothesis	Assumed Treatment Effect	Power
------------	--------------------------------	-------

	(Common SD)	
Primary:	-16.7 (50)	96%
Change from baseline in mean monthly hours of at least moderate headache pain intensity over months 1, 2, and 3		
Secondary: Change from baseline in mean monthly		
MFIQ physical function domain score over months 1, 2, and 3	-9.2 (18.0)	> 99%
MFIQ usual activities domain score over months 1, 2, and 3	-7.5 (19)	> 99%
MFIQ emotional function domain score over months 1, 2, and 3	-11.5 (22)	> 99%
MFIQ social function domain score over months 1, 2, and 3	-6.9 (20)	97%
Average duration of at least moderate migraine pain intensity in migraine attacks occurring over months 1, 2, and 3 ^a	-2.0 (8)	81%
Average peak migraine pain intensity over months 1, 2, and 3	-0.11 (0.44)	81%

MFIQ = Migraine Functional Impact Questionnaire

Note: All power calculations are based on a 2-sided significance level of 0.05. The assumed treatment effects and common standard deviations are derived or chosen from a subset of placebo-treated and erenumab-140mg-treated subjects in erenumab Study 20120296 with high-frequency episodic migraine (ie, 7 to 14 monthly migraine days) and having at least 4 moderate-to-severe migraine attacks at baseline. ^a If a subject did not have any migraine attacks in a given month, the duration of at least moderate migraine pain intensity **was counted as 0**.

4. Covariates and Subgroups

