4.2 Subgroups

The primary and secondary endpoints of the M-DBTP will be analyzed in the following subgroups:

- Number of prior treatment failures (1, 2, and 3 or more treatment failures)
- Medication overuse status at baseline (yes vs. no)

Selected exploratory endpoints of the E-DBTP for the first qualifying triptan-treated attack may be analyzed by medication overuse status at month 3 (yes vs. no) (see Section 9.5.3).

The subgroups will be re-examined for appropriateness and may be re-categorized (due to small sample size, for example, if there are < 10% of subjects within a subgroup) before unblinding.

5. Definitions

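### The primary and secondary model omits two collected baseline factors, prior preventive failures and medication overuse; adding them would be a small efficiency gain, not the repair of an error

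*SAP*

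**What the plan says.** SAP 9.5.1 fixes the terms for the primary and secondary endpoints: "The model will include treatment, scheduled visit, treatment by visit interaction, and baseline value as covariates". SAP 4.1, SAP Tables 9-1 and 9-2, Protocol 9.3.2 and the methods table in Protocol 9.4.2 agree with it. For months 1 to 3 the only baseline adjustment is the endpoint's own baseline value, with one slope for all three visits. SAP 4.1 allows further covariates, month 3 medication overuse among them, only for month 4 endpoints.

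SAP 4.2 names two subgroup factors for these same endpoints: "Number of prior treatment failures (1, 2, and 3 or more treatment failures") and "Medication overuse status at baseline (yes vs. no"). SAP 9.5.1 uses them for within-subgroup estimates and interaction tests, not to adjust the overall comparison, and plans no sensitivity analyses.

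On allocation, Protocol 6.4.1 states: "Subjects will be randomized in a 1:1 allocation ratio to either erenumab or placebo in a double-blind manner". It mentions no stratification factor.

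SAP Table 3-1 plans 96% power for the primary, 97% to above 99% for the four MFIQ domains, and 81% each for average duration and average peak pain intensity. In SAP 9.1 those last two are steps 3 and 4 of the fixed testing sequence.

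**The concern.** A baseline factor that predicts outcome beyond the endpoint's own baseline value reduces residual variance when it is in the model. It also takes out the part of the treatment difference that is due to chance imbalance in that factor. In a linear model the treatment effect being estimated stays the same.

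Both factors should be available for almost everyone. At least one prior failure is an entry criterion (Protocol 5.1, criterion 106). Baseline diary compliance of at least 80% is required (criterion 111), well above the 14 diary days that the SAP needs to derive medication overuse.

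What is at stake is a modest amount of power for the two endpoints with the least margin. They are tested last, so each counts only if everything before it has succeeded. Protocol 4.2.1 rules out replacing withdrawn subjects. An adjusted model would be credible only if it is fixed before unblinding.

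**Working it through.** **Inputs.** SAP 3.2 states "All power calculations are based on a 2-sided significance level of 0.05" and "288 subjects per group including 10% dropouts", so evaluable n = 288 × 0.9 = 259 per arm. Effects and SDs come from SAP Table 3-1: duration −2.0 (8), peak intensity −0.11 (0.44), primary −16.7 (50), MFIQ social −6.9 (20).

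**Reproducing the plan.** Duration and peak intensity share a standardised effect: 2.0/8 = 0.11/0.44 = 0.25. The noncentrality is 0.25 × √(259/2) = 2.845. The normal approximation gives Φ(2.845 − 1.960) = 81.2%, and the noncentral t gives 81.05%; the plan says 81%. For the primary, 0.334 × 11.380 = 3.801 and Φ(1.841) = 96.7% (stated 96%). MFIQ social gives 97.5% (stated 97%). The other three domains are above 99%, as stated.

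**Adding covariates.** Let R² be the share of residual variance, beyond the baseline value, that the added factors explain. The SD becomes SD × √(1 − R²), and the interval narrows by 1 − √(1 − R²). R² is an assumption. Power below is for each of the two 81% endpoints.

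| R² | Power (noncentral t) | Interval narrower by | Equivalent evaluable n per arm, 259/(1 − R²) |
|---|---|---|---|
| 0 | 81.05% | – | 259 |
| 1% | 81.4% | 0.5% | 262 |
| 2% | 81.8% | 1.0% | 264 |
| 5% | 83.0% | 2.5% | 273 |
| 10% | 84.9% | 5.1% | 288 |

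By the normal approximation, the primary moves from 96.7% to 97.4% at R² 5% and 98.0% at 10%. MFIQ social moves from 97.5% to Φ(3.926/√0.95 − 1.960) = 98.1% at 5%.

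**What R² is plausible.** A two-level factor with prevalence q and a residual mean difference of d within-group SDs explains q(1 − q)d² / (1 + q(1 − q)d²). With q = 0.3 and d = 0.2 this is 0.0084/1.0084 = 0.8%; with q = 0.5 and d = 0.3 it is 0.0225/1.0225 = 2.2%. That is about 0.3 to 1 power point per such factor. Two factors of this kind make 2% to 5% a fair expectation and 10% optimistic.

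**Charge for the extra terms.** Prior failures in three categories takes 2 degrees of freedom and overuse takes 1. If they explained nothing, the variance of the treatment contrast would rise by about 3/518 = 0.6%, or roughly 0.3% in standard error. The table is before this charge, so an R² of 1% is only just above break-even.

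**Common baseline slope.** This was simulated with three visits, first-order autoregressive correlation of 0.4 or 0.7 (taken as known), 259 per arm, 0% or 10% dropout, and true slopes either equal or falling as steeply as 0.7, 0.5, 0.3. Allowing a separate slope at each visit changed the standard error of the months 1 to 3 average by 0.3% or less (ratios 0.997 to 1.000).

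**Joint success.** Assume independent tests and take the MFIQ step as passed. The chance of winning on primary, duration and peak is then 0.967 × 0.812 × 0.812 = 64% as planned, and 0.974 × 0.831 × 0.831 = 67% at R² 5%. Positive correlation between endpoints would raise both.

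**The case against.** The strongest reply is that nothing here is wrong. Protocol and SAP agree on one prespecified model, and under randomisation it gives a valid test whose standard error already allows for chance imbalance. That stands. A reader might infer that unstratified, unadjusted allocation biases the result. It does not; and the absence of stratification is itself inferred from the protocol's silence.

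Second, the documents never show that either factor is prognostic. The SAP lists them to look for variation in the treatment effect, which is a different property. This stands too, and is why R² appears only as an assumed range.

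Third, a reader might conclude that the secondary endpoints as a group are thinly powered, or that the common slope wastes precision. The documents do not support the first, since four of the six hypotheses are at 97% or more. The simulation does not support the second for the months 1 to 3 average.

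Fourth, the 81% may be conservative. SAP 3.2 takes the planning SDs from a subset of an earlier study without saying whether they are raw or baseline-adjusted. If raw, the baseline term already in the model may lift power above 81%.

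Fifth, the change touches more than one sentence: the protocol fixes the same covariates, subgroup categories may be recut before unblinding, and within-subgroup analyses reuse the primary model. These are drafting costs and do not make the change harmful.

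**Conclusion.** The point holds as an efficiency recommendation of low severity. The model leaves out two baseline factors that the trial collects and has already categorised for the same endpoints. Adding them would probably raise power for average duration and average peak intensity by 1 to 2 points each (R² 2% to 5%), with about 4 points at R² 10% as an optimistic bound. The gain for the other five hypotheses is small. These sizes rest on an assumed R², on 259 evaluable subjects per arm, and on planning SDs of unstated type. The documents do not support reading this as a flaw in validity, or as a shortfall in the plan's stated power, which reproduces.

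**What to change.** Before unblinding, add number of prior preventive failures (1, 2, 3 or more) and baseline medication overuse (yes/no) as main effects to the mixed model for the primary and secondary endpoints. In the same edit:

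- Use whatever categories are final before unblinding, so that any recut for small groups carries through to the model.
- Leave each factor out of the model when analysing within its own strata, where it is constant.
- List the change in SAP section 10, which now declares one deviation, because Protocol 9.3.2 and the methods table in Protocol 9.4.2 name only the baseline value.

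Two further terms are optional. Region could be derived from site (Protocol 4.2.2: "Approximately 76 investigative sites in North America and Europe will be included in the study"), but the SAP does not use it as a covariate or subgroup. A baseline-by-visit interaction may improve the fit of the by-visit estimates that SAP 9.5.1 tabulates, but it adds almost no precision to the months 1 to 3 average.

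The cost is three degrees of freedom out of more than 500, a few sentences of SAP text, and a declared departure from the protocol's covariate list. No extra subjects or data are needed.
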